4.2. Variable Definitions

The following variables will only be calculated if not reported on the CRF.

4.2.1. Age

Subject age will be calculated as the integer part of the number of years from date of birth to the date of signing the informed consent form, using the following formula:

$$\text{Age} = \text{integer part of (date of informed consent} - \text{date of birth} + 1) / 365.25$$

4.2.2. Prior and Concomitant Medication

Prior medication is defined as any nonstudy medication started before the first dose of itacitinib.

Concomitant medication is defined as any nonstudy medication that is started accordingly:

- Before the date of first administration of itacitinib and is ongoing throughout the study or ends on/after the date of first study drug administration.
- On/after the date of first administration of itacitinib and is ongoing or ends during the course of study drug.

A prior medication could also be classified as "both prior and concomitant" if the end date is on or after first dose of itacitinib. In the listing, it will be indicated whether a medication is prior-only, concomitant-only, or both prior and concomitant.

For the purposes of analysis, all medications will be considered concomitant medications unless the medications can unequivocally be defined as not concomitant.

5. STATISTICAL METHODOLOGY

5.1. General Methodology

Unless otherwise noted, SAS® software (SAS Institute Inc, Cary, NC; Version 9 or later) will be used for the generation of all tables, graphs, and statistical analyses. Descriptive summaries for continuous variables will include, but not be limited to, the number of observations, mean, standard deviation, median, minimum, and maximum. Descriptive summaries for categorical variables will include the number and percentage of subjects in each category.

5.2. Treatment Groups

This is an open-label Phase 2 study with 2 cohorts. Subjects will be summarized overall and by cohort. Planned cohorts for this study are as follows:

- **Cohort A:** 200 mg QD itacitinib + ruxolitinib.
- **Cohort B:** 600 mg QD itacitinib monotherapy.

5.3. Analysis Populations

5.3.1. Full Analysis Set

The FAS includes all subjects enrolled in the study who received at least 1 dose of itacitinib.

The FAS will be used for the summary of demographics, baseline characteristics, subject disposition, and analyses of all efficacy data.

5.3.2. Extension Population

The extension population includes all subjects in the FAS population who continued into the extension period of the study and received at least 1 dose of itacitinib after entering the extension period.

5.3.3. Safety Population

The safety population includes all enrolled subjects who received at least 1 dose of itacitinib. Treatment cohorts for this population will be determined according to the actual treatment the subject received regardless of assigned study drug treatment.

All safety analyses will be conducted using the safety population.

5.3.4. Ruxolitinib-Treated Population

The ruxolitinib-treated population includes all subjects in the safety population who received at least 1 dose of ruxolitinib on or after Day 1 (ie, the first day of itacitinib administration).

5.3.5. Pharmacokinetic [REDACTED] Evaluable Population

The PK evaluable population will include all subjects who received at least 1 dose of itacitinib and provided at least 1 postdose plasma sample for PK. The study pharmacokineticist will

review data listings of study drug administration and sample records to identify subjects to be excluded from analyses of PK data.

6. BASELINE, EXPOSURE, AND DISPOSITION VARIABLES AND ANALYSES

[Appendix A](#) provides a list of data displays. Shells for data displays are provided in a separate document.

6.1. Baseline and Demographics, Physical Characteristics, and Disease History

6.1.1. Demographics

[figure not shown]
The following demographics will be summarized for the FAS population: age, sex, race, ethnicity, weight, and height.

6.1.2. Baseline Disease Characteristics

The following baseline disease characteristics will be summarized for the FAS population: ECOG performance status.

6.1.3. Disease History

Time since diagnosis, MF disease type (primary MF, post-PV–MF, post-ET–MF), IWG-MRT Risk Category (Low, Intermediate-1, Intermediate-2, High-risk) at diagnosis and screening, MF grade at diagnosis and screening, 

 largest percentage reduction in spleen by palpation during ruxolitinib treatment, largest percentage volume reduction in spleen by CT or MRI during ruxolitinib treatment, prior transfusions for MF (Y/N), and transfusion dependency at baseline (Y/N) will be summarized for all subjects in the FAS population.

Time since diagnosis will be calculated as:

$$\text{Time since diagnosis (years)} = (\text{Day 1 date} - \text{date of diagnosis} + 1) / 365.25.$$

6.1.4. Prior Therapy

Subjects' ruxolitinib treatment history will be summarized, including the maximum daily dose of ruxolitinib (in mg) administered, total daily dose of ruxolitinib (in mg) prescribed at screening for subjects in Cohort A, and duration of ruxolitinib treatment.

Prior systemic MF therapy treatments will be summarized for all subjects in the FAS population. Component drugs, start and stop date, and reason for discontinuation will be listed.

Number of subjects who received prior splenic radiation or prior hematopoietic stem cell transplant will be summarized for the FAS population.

6.1.5. Medical History

For subjects in the FAS population, medical history will be summarized by assigned treatment cohort. This summation will include the number and percentage of subjects with significant medical history for each body system/organ class as documented on the CRF.

6.2. Disposition of Subjects

The number and percentage of subjects who were treated, completed study treatment through Week 24, discontinued study treatment prior to Week 24 with a primary reason for discontinuation, continued into the extension period, discontinued study treatment during the extension period with a primary reason for discontinuation, and discontinued from the study with a primary reason for withdrawal will be summarized for the FAS population. The number of subjects enrolled by site will also be provided by treatment cohort.

6.3. Protocol Deviations and Violations

Protocol deviations and violations recorded on the CRF will be presented in the subject data listings.

6.4. Exposure

For subjects in the safety population, exposure to itacitinib and ruxolitinib will be summarized descriptively as the following:

- **Duration of treatment with itacitinib (days):** date of last dose of itacitinib – date of first dose of itacitinib + 1. For subjects who are continuing to receive itacitinib at the time of the analysis, the date of the last visit will be used.
Average daily dose of itacitinib (mg/day): total actual itacitinib dose taken (mg) / duration of treatment with itacitinib (days). Total actual dose of itacitinib will be calculated based on the information entered on the drug accountability CRF.
- **Itacitinib dose modifications:** Number of subjects who had itacitinib dose reductions or interruptions will be summarized.
- **Duration of treatment with ruxolitinib (days):** date of last dose of ruxolitinib – date of first dose of on-study ruxolitinib + 1. For subjects who are continuing to receive ruxolitinib at the time of the analysis, the date of the last visit will be used.
- **Average daily dose of ruxolitinib (mg/day):** total actual on-study ruxolitinib dose taken (mg) / duration of treatment with ruxolitinib (days).
- **Ruxolitinib dose modifications:** Number of subjects who had ruxolitinib dose reductions or interruptions on-study will be summarized.

6.5. Study Drug Compliance

For subjects in the safety population, overall compliance (%) for itacitinib will be calculated for all subjects as

$$\text{compliance (\%)} = 100 \times [\text{total dose actually taken}] / [\text{total prescribed dose}].$$

The total prescribed dose is defined as the sum of the doses prescribed by the investigator accounting for dose modifications.

The total actual dose taken will be calculated based on information entered on the drug accountability CRF. If there is dispensed drug that has not been returned yet, the actual dose taken starting from the dispense date of the unreturned drug will be imputed by the dose taken as reported on the dosing CRF.

Compliance for ruxolitinib will not be calculated.

6.6. Prior and Concomitant Medication

For subjects in the safety population, prior medications and concomitant medications will be coded using the WHO Drug Dictionary and summarized by WHO drug class and WHO drug term. Results will be summarized as number and percentage of subjects with prior and concomitant medications by PT and WHO drug class.

7. EFFICACY

[Appendix A](#) provides a list of data displays. Shells for data displays will be provided in a separate document.

7.1. General Considerations

7.2. Efficacy Hypotheses

The primary hypothesis is that itacitinib, in combination with low-dose ruxolitinib or as monotherapy for subjects who progressed after initial spleen reduction (either volume by MRI/CT or length by palpation) on ruxolitinib, will achieve a median percentage SVR of > 0% at Week 24 in either Cohort A or Cohort B.

7.3. Analysis of the Primary Efficacy Parameter

7.3.1. Primary Efficacy Analysis

The primary endpoint of change and percentage change of SVR (as measured by MRI or CT) at Week 24 will be summarized by cohort. Within each cohort, the sign test will be used to evaluate whether the median percentage of SVR is > 0%. For purposes of this test, subjects with missing Week 24 evaluations who discontinued prior to the planned Week 24 visit will be considered as not having achieved SVR. If 21 subjects are enrolled in a cohort, the null hypothesis of $\leq 0\%$ median SVR will be rejected if 15 or more out of 21 subjects observe a $> 0\%$ SVR at Week 24.

The baseline spleen volume will be assessed between Study Day -7 and Day 1 (inclusive) with the last value in the assessment window used if there are multiple values measured during this period. Subjects with missing baseline spleen volume will not be evaluable for this analysis. The Week 24 spleen volume will be assessed during Week 24 (Day 168 ± 7), and the last value in the assessment window will be used if there are multiple values measured during the Week 24 visit.

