3.2. Control of Type I Error

The level of significance for detecting a difference from a 0% median percentage SVR in each cohort is 5% (1-sided). In other words, under the null hypothesis of subjects receiving itacitinib having a true median percentage SVR of 0%, there is a 5% chance of declaring a given cohort as having a median percentage $SVR > 0\%$. Note that this level of significance does not account for testing of multiple cohorts.

All other statistical analyses are exploratory in nature. Unless otherwise specified, all CIs provided will be at the 95% confidence level.

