3.3. Sample Size Considerations

Up to 21 subjects will be enrolled in each of the 2 dose cohorts (Cohort A and Cohort B) for a total of 42 subjects overall. The sign test will be used to evaluate percentage change from baseline in spleen volume by MRI or CT at Week 24 in applicable subjects with a 1-sided Type I error of 0.05. If 15 or more out of 21 subjects observe a $> 0\%$ SVR at Week 24, then further development of itacitinib as monotherapy or in combination with ruxolitinib may be considered. If the percentage of SVR at Week 24 is normally distributed with mean 11.4 and standard deviation 14.5, the test has 85% power to indicate that additional development is warranted.

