4.1.4. Handling of Missing and Incomplete Data

In general, values for missing data will not be imputed unless methods for handling missing data are specified in this section or relevant sections.

Partial MF diagnosis date will be handled as follows:

- If only the day is missing, then the imputed day will be the first of the month.
- If both the month and day are missing, then the imputed day and month will be 01 JAN.

- No imputation will be done if the date is completely missing.

Missing or partial date of last dose will be handled as follows:

- If only the day is missing, then the imputed date of the last dose will be the earlier date of the first day of the month or the date that the subject discontinued treatment.
- Otherwise, the date that the subject discontinued treatment will be used as the date of the last dose.

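### Does tying the 15-of-21 rejection count to the number enrolled leave the primary decision rule open when some subjects drop out of the sign test?

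*SAP*

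**What the plan says.** Section 3.2 sets the significance level at 5%, one-sided, separately for each cohort. Section 3.3 names the sign test on percentage change in spleen volume at Week 24, sets the size ("Up to 21 subjects will be enrolled in each of the 2 dose cohorts") and gives 85% power if SVR is normal with mean 11.4 and standard deviation 14.5. If the count of 15 out of 21 is reached, "then further development of itacitinib as monotherapy or in combination with ruxolitinib may be considered".

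Section 7.3.1 repeats that the sign test is applied within each cohort and adds the numerical rule. It opens with "If 21 subjects are enrolled in a cohort, the null hypothesis of" a median SVR no greater than zero, and continues that this null "will be rejected if 15 or more out of 21 subjects observe a" positive SVR at Week 24.

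Missing data are handled in three places:

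- **Missing baseline (7.3.1):** "Subjects with missing baseline spleen volume will not be evaluable for this analysis".
- **Missing Week 24 after discontinuation (7.3.1):** "subjects with missing Week 24 evaluations who discontinued prior to the planned Week 24 visit will be considered as not having achieved SVR".
- **Everything else (4.1.4):** "values for missing data will not be imputed unless methods for handling missing data are specified in this section or relevant sections".

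Section 5.3.1 limits the Full Analysis Set to enrolled subjects who took at least one dose of itacitinib.

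**The concern.** The count is conditional on the number enrolled, but the test runs on the number evaluable. A cohort can have 21 enrolled and fewer than 21 in the test, because a subject has no baseline volume or was never dosed. The SAP gives no cut-off for that situation and does not say in words whether the count or the 5% test decides. With 14 responders among 19 evaluable subjects, the test would reject and a literal requirement of 15 would not.

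A second gap seems to sit beside it. A missing Week 24 value is made a failure only for subjects who discontinued. A subject still on study with no scan in the Day 168 ± 7 window is not mentioned, and how that subject is handled also affects n.

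This is the only formal test in the SAP, and it informs whether development continues. In an open-label, sponsor-unblinded study, a rule settled after the data are seen would be a fair worry.

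**Working it through.** **Inputs.** One-sided 5% (Section 3.2); sign test, n = 21, mean 11.4, SD 14.5, stated power 85% (Section 3.3); cut-off 15 (Sections 3.3 and 7.3.1).

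**Step 1: reproduce the plan's figure.** The probability that a subject has SVR above zero is Φ(11.4/14.5) = Φ(0.786) = 0.784. For 21 subjects:

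- type I error: P(Bin(21, 0.5) ≥ 15) = 0.039;
- power: P(Bin(21, 0.784) ≥ 15) = 0.852, which matches the stated 85%;
- one fewer: P(Bin(21, 0.5) ≥ 14) = 0.095, above 5%.

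So 15 is exactly the one-sided 5% sign-test cut-off at n = 21. It is the test's own critical value, not a separate rule.

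**Step 2: what the test gives for smaller n.** The cut-off is the smallest c with P(Bin(n, 0.5) ≥ c) ≤ 0.05. The last two columns keep 15 regardless of n.

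| n in test | exact cut-off | type I error | power | type I error, 15 held | power, 15 held |
|---|---|---|---|---|---|
| 21 | 15 | 0.039 | 85.2% | 0.039 | 85.2% |
| 20 | 15 | 0.021 | 74.9% | 0.021 | 74.9% |
| 19 | 14 | 0.032 | 78.8% | 0.010 | 60.7% |
| 18 | 13 | 0.048 | 82.5% | 0.004 | 43.4% |
| 17 | 13 | 0.025 | 70.2% | 0.001 | 25.6% |

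With one subject out, the two readings coincide. From two out they can differ. The type I error stays below 5% under either.

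**Step 3: how often the readings could differ.** The SAP gives no rate of unevaluable subjects, so the rate q is an assumption. Take 21 enrolled, the number unevaluable as Bin(21, q) independent of response, and the SAP's own effect.

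| q | P(two or more out) | P(readings disagree) | power, exact test | power, 15 held |
|---|---|---|---|---|
| 1% | 1.9% | 0.4% | 83.3% | 82.9% |
| 2% | 6.5% | 1.4% | 81.9% | 80.5% |
| 5% | 28.3% | 7.1% | 79.6% | 72.5% |
| 10% | 63.5% | 20.6% | 78.0% | 57.4% |

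**Step 4: which reading the text supports.** The 15-of-21 sentence names its own denominator. With 19 in the test there is no count out of 21, so applying 15 to 19 means ignoring half of the sentence. The sign test at one-sided 5% is stated without any condition on n. If fewer than 21 are enrolled, the sentence's opening condition fails and only the test is left, so enrolment short of 21 creates no conflict at all.

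**Step 5: the missed scan on study.** Section 4.1.4 imputes nothing unless a method is given, and Section 7.3.1 gives one only for subjects who discontinued. A subject still on study with no Week 24 scan is therefore not imputed and leaves the test. Section 11 is consistent with this: it defines failure as discontinuation before the Week 24 assessment or a measured SVR of zero or less. The alternative, counting such subjects as failures at n = 21, compares as follows:

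- one missed scan: P(Bin(20, 0.784) ≥ 15) = 74.9% as a failure; 74.9% if left out;
- two missed scans: P(Bin(19, 0.784) ≥ 15) = 60.7% as failures; 78.8% if left out (14 of 19).

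**The case for a change.** The strongest case for a change is that deriving a cut-off requires a settled n, and that the SAP nowhere says that the test overrides the printed count. Losing subjects is also plausible on the SAP's own terms. Section 7.3.1 sets a baseline window of Day -7 to Day 1 that is narrower than the general rule in Section 4.1.3, so a scan on Day -8, read literally, leaves a subject without a baseline. Appendix A labels the Week 24 responder table as FAS, although Section 7.3.1 removes some FAS subjects from the test. The remedy would cost only wording.

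Part of this stands. No cut-off below 21 is printed, the number in the test can fall short of the number enrolled, and the arithmetic of the disagreement is right. What does not stand is that the rule is open. The test, its level and its sidedness are all stated, and n follows from the missing-data provisions. Making on-study missed scans failures would also be more than a clarification. It would replace the SAP's default with a stricter rule, whose power with two such subjects is the same 61% that is objected to when 15 is held at n = 19.

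**Conclusion.** No change is needed. The point is a missing detail that an analyst fills in only one sensible way: apply the exact one-sided 5% sign test to the evaluable subjects and read 15 of 21 as its n = 21 case. Conflict with the printed count requires 21 enrolled and at least two outside the test, and a strained reading of the sentence as well. If someone did hold 15, the error would be conservative. The loss would be about 18 percentage points of power at n = 19 (78.8% − 60.7%) and 39 at n = 18 (82.5% − 43.4%), with no gain in false positives. The chance that the readings disagree runs from 0.4% to 20.6% for assumed unevaluable rates of 1% to 10%. The SAP supports no particular rate, and the upper figure comes entirely from the 10% assumption.

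How to treat an on-study missed scan is a trade-off on which the SAP has taken a position. Counting such subjects as failures could be shown as a sensitivity analysis, but its absence is not an error. The calculations rest on the SAP's normal model for SVR and on missingness unrelated to response.

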7.3.2. Subgroup Analyses for Primary Endpoint

Subgroups will be formed based on the following subject characteristics and baseline variables for those subjects whose data are available. Note that all subgroup analyses are descriptive in nature.

- IWG Risk Category at screening (Low, Intermediate-1, Intermediate-2, High-risk)
- MF grade at screening (MF-0, MF-1, MF-2, MF-3)
- Transfusion-dependent at screening (Y/N)
- MF Disease Type (Primary MF, Post-PV–MF, Post-ET–MF)
- Sex (M/F)
- Race (Caucasian, Black, Asian, All Others, Unspecified)
- ECOG status at baseline (0, 1, 2)

7.4. Analysis of the Secondary Efficacy Parameters

7.4.1. Other Spleen Volume Reduction Analyses

Week 12 spleen volume, along with change and percentage change in SVR, will be assessed during Week 12 (Day 84 ± 7) using approaches outlined in Section 7.3.1.

For all scheduled spleen volume assessments (ie, Weeks 12, 24, 36, 48, etc), median percentage SVR will be calculated by cohort with associated 2-sided 90% exact binomial CI estimated.

7.4.2. Change and Percentage Change From Baseline in Spleen Length

Change and percentage change in spleen length from baseline as measured by palpation at each visit where the parameter is assessed through Week 24 will be tabulated by cohort with summary statistics.

7.4.3. MFSAF v2.0 and Total Symptom Score

The daily TSS for MFSAF v2.0 is determined on a study day basis and is the sum of the 6 individual symptom scores as measured by the daily symptom diary excluding the score for degree of inactivity. Included items are itching, night sweats, abdominal discomfort/bloating, early satiety, pain under the ribs on left side and bone/muscle pain. If any of the 6 components of the score are missing, then the daily TSS is missing on that day. Observations with missing dates will be excluded from the analysis.

The TSS for baseline, Week 12, and Week 24 will be determined by averaging the daily TSS for the days between the start and end of windows as described in [Table 2](#). The TSS for Weeks 4, 8, 16, and 20 will be derived in a similar fashion using the first nonmissing daily TSS available between

Day ($7 \times \text{week}$)

and

Day ($7 \times \text{week}$) + 7

as the end of the window.

Table 2: Windows for Deriving Total Symptom Score for Baseline, Week 12, and Week 24

Period	Start of Window	End of Window	Missing
Baseline	7 days on or prior to end of window	Last day a daily TSS was collected between Day -7 and Day -1 (inclusive)	4 or more missing out of the 7 daily TSSs in the window; or no measurement between Day -7 and Day -1
Week 12	7 days on or prior to end of window	First day a daily TSS was collected between Day 84 and Day 90 (inclusive)	4 or more missing out of the 7 daily TSSs in the window; or no measurement between Day 84 and Day 90
Week 24	7 days on or prior to end of window	First day a daily TSS was collected between Day 168 and Day 174 (inclusive)	4 or more missing out of the 7 daily TSSs in the window; or no measurement between Day 168 and Day 174

The percentage change at Week 4, 8, 12, 16, 20, and 24 will be calculated using the formula

$$\% \text{ change} = 100 \times (\text{Week xx total score} - \text{baseline total score}) / \text{baseline total score}$$

and will be summarized with descriptive statistics (mean, standard deviation, etc).

Summaries for the 7 individual scores will be provided using the same windows used for the TSS.

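### MFSAF total symptom score: Table 2 lists Week 12 and Week 24 end days that can never give a score, and fixing the end day at the first diary score discards usable weeks

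*SAP*

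**What the plan says.** SAP Section 7.4.3 builds each visit's MFSAF v2.0 total symptom score (TSS) from daily diary totals. A daily total needs all six items: "If any of the 6 components of the score are missing, then the daily TSS is missing on that day".

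Table 2 then sets three things for each visit:

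- **End of window.** Week 12: "First day a daily TSS was collected between Day 84 and Day 90 (inclusive". Week 24: "First day a daily TSS was collected between Day 168 and Day 174 (inclusive". Baseline runs the other way: "Last day a daily TSS was collected between Day -7 and Day -1 (inclusive".
- **Start of window.** "7 days on or prior to end of window".
- **Missing.** Week 12: "4 or more missing out of the 7 daily TSSs in the window; or no measurement between Day 84 and Day 90". Week 24: "4 or more missing out of the 7 daily TSSs in the window; or no measurement between Day 168 and Day 174".

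Weeks 4, 8, 16 and 20 use the same first-score approach, but the end day may fall anywhere from Day 7 x week to Day 7 x week + 7. That is eight candidate days, against seven in Table 2. The seven individual item scores use the same windows as the TSS. Section 7.4.3 gives no fallback when the chosen window fails the completeness rule.

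**The concern.** The end-day rule and the completeness rule work against each other. The end day is the first day in the range with a score, so every earlier day in the range has no score. Those empty days lie inside the look-back and count against the subject. The later the first score, the more of the 7-day window is empty by construction. From the fifth listed day on, the completeness rule cannot be met.

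The same choice does harm when the first score is early. Once a score exists on Day 84, the window is fixed at Days 78 to 84, and nothing recorded on Days 85 to 90 can help, however complete it is.

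At stake is the number of evaluable subjects for a listed secondary endpoint, symptom change at Weeks 12 and 24, in cohorts of at most 21 (Section 3.3). Section 4.1.4 says that missing values are in general not imputed, so a score lost through the window rule stays lost. The loss also carries into the individual item summaries.

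**Working it through.** The plan states no completion rate and no expected number of evaluable scores, so there is no figure to reproduce. The check has two parts: logic that needs no assumption, and a size that does.

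**1. End days that cannot work.** Let the first scored day be E = 84 + j, with j = 0 to 6. The window is Days E-6 to E. Days 84 to E-1 are empty and lie inside it, so at least j days are missing.

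| End day (Week 12 / Week 24) | 84 / 168 | 85 / 169 | 86 / 170 | 87 / 171 | 88 / 172 | 89 / 173 | 90 / 174 |
|---|---|---|---|---|---|---|---|
| Fewest possible missing days | 0 | 1 | 2 | 3 | 4 | 5 | 6 |
| Can give a TSS? | yes | yes | yes | yes | no | no | no |

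Enumerating every present/missing pattern over Days 77 to 90 confirms this: none of the 512, 256 and 128 patterns with first score on Day 88, 89 or 90 is evaluable. Reading the look-back as eight days (E-7 to E) gives the same zeros. At Weeks 4, 8, 16 and 20 the range has offsets 0 to 7, and the last four (4 to 7) fail in the same way.

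**2. Two subjects who lose a score.**

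- Scores on Days 78 to 83 and 88 to 90. The rule sets E = 88, window 82 to 88, with 3 of 7 scores: missing. Days 78 to 84 hold 6 of 7.
- No scores on Days 78 to 83, all of Days 84 to 90 scored. The rule sets E = 84, window 78 to 84, with 1 of 7: missing. Days 84 to 90 hold 7 of 7.

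**3. Size, assuming each day is completed independently with probability p.** Given E = 84 + j, the subject has the score on E plus whatever falls on the 6 - j look-back days before Day 84, and needs at least 3 of those:

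P(evaluable) = sum over j = 0 to 6 of (1-p)^j x p x P(Bin(6-j, p) >= 3).

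This is P(Bin(7, p) >= 4) split by the position of the first success. So, under this assumption, the rule gives exactly the evaluable share of a fixed Day 78 to 84 window with the same 4-of-7 standard. At p = 0.8 the terms are 78.64 + 15.07 + 2.62 + 0.33 + 0 + 0 + 0 = 96.67%.

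The share with first score on Days 88 to 90 is (1-p)^4 x [1 - (1-p)^3]. At p = 0.8: 0.0016 x 0.992 = 0.16%.

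The alternative ends the window on the first day in Days 84 to 90 whose 7-day look-back holds at least 4 scores. Its share comes from exact enumeration of all patterns on Days 78 to 90.

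| Daily completion p | 80% | 70% | 60% | 50% |
|---|---|---|---|---|
| Plan (= fixed Days 78-84) | 96.7% | 87.4% | 71.0% | 50.0% |
| Alternative rule | 99.9% | 98.6% | 93.3% | 80.0% |
| Gain, points | 3.2 | 11.2 | 22.3 | 30.0 |
| Gain x 21 subjects | 0.7 | 2.4 | 4.7 | 6.3 |
| First score on Days 88-90 | 0.16% | 0.8% | 2.4% | 5.5% |
| Gain from subjects with first score on Days 84-87, points | 3.1 | 10.6 | 20.9 | 27.9 |

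About 93 to 96% of the gain comes from subjects whose first score is on Days 84 to 87, that is, from the lock and not from the unreachable end days. At 90% completion the plan already gives 99.7%. No pattern that is evaluable under the plan becomes missing under the alternative.

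**The case against.** The strongest reply is that little is lost against ordinary practice. The rule matches a plain fixed Day 78 to 84 window, so the shortfall comes from the 4-of-7 standard, which nobody disputes. Any rule that searches seven candidate windows must beat a rule that uses one. The endpoint is descriptive, Section 3.2 calls all analyses beyond the primary test exploratory, and the MPN-SAF gives a second symptom measure at the same weeks.

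Most of this stands as a limit on size. It does not rescue the rule. Table 2 offers seven end days, evidently to tolerate diary gaps, yet three cannot work and the allowance buys no evaluable subjects on average. The subject with all of Days 84 to 90 scored meets the plan's own standard inside the plan's own range and is still set to missing.

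A reader might infer several stronger points that the document does not support:

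- **That the whole rule fails.** It works for end days 84 to 87.
- **That the unreachable days cause the loss in the table.** They account for little of it.
- **That a subject with diaries only from Day 88 is wrongly excluded.** That subject has at most 3 scores by Day 90, below the 4-of-7 standard.
- **That the diary window conflicts with the spleen-scan window.** Section 7.3.1 says "The Week 24 spleen volume will be assessed during Week 24 (Day 168 ± 7"), but this times an MRI or CT, and nothing in the SAP says the daily diary stops at the scan.
- **That the symptom result is biased.** Irregular completers are lost more often under any completeness threshold. The SAP gives nothing from which to derive a direction or size.

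**Conclusion.** The rule is wrong as written, with modest consequences. That end days 88 to 90 and 172 to 174, and the last four of eight at Weeks 4, 8, 16 and 20, can never give a TSS is exact and needs no assumption. So is the loss of a subject with a full scored week on Days 84 to 90.

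The size depends on assumed independent completion at a constant daily rate, which the SAP does not give. On that basis the avoidable loss is about 3 points at 80% completion and 11 points at 70%, or under 1 and about 2 subjects in a cohort of 21 if all 21 are still keeping a diary. It is negligible at 90%. Real gaps tend to cluster, so these figures are illustrative. The primary sign test is untouched. The change is worth making because it recovers secondary-endpoint data already collected, at almost no cost.

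**What to change.** In Table 2, define the end of the window as the first day in Days 84 to 90 (Week 24: Days 168 to 174) whose 7-day look-back, end day included, contains at least 4 nonmissing daily TSSs. Set the TSS to missing only if no such day exists. State the window as Days E-6 to E so that it cannot be read as eight days. Apply the same rule at Weeks 4, 8, 16 and 20 with one common range, Day 7 x week to +6, which also removes the +6 versus +7 difference between visits.

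The end day then need not itself carry a score, so the separate clause requiring a measurement in the range falls away. Subjects with no score in the range but at least 4 on Days 78 to 83 become evaluable at Day 84.

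The cost is a table edit and a small change to the derivation. Some windows end up to 6 days later than now. A few that are evaluable today end up to 3 days earlier, where Day 84's look-back already holds 4 scores but the first score in the range falls on Days 85 to 87.
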